6.3.2 PREPARATION AND UTILIZATION

Baseline data as well as compression session data will be captured using the dedicated BIOPAC data acquisition system. A laptop running Windows OS will be provided containing the BSL 4.1 software bundle. To launch the software, double click on the BSL 4.1 (BIOPAC) software icon on the desktop.

- The operator will load a pre-set template located on the study laptop
- During data capture, the clinical operator/technician can use specific function keys to tag events during the ECP session, including:
 - F1 key to tag Start Baseline,

- F2 key to tag End Baseline,
 - F3 key to tag Start of Wave PRO compressions,
 - F4 key to tag End of Wave PRO compressions
 - ESC key to tag any other miscellaneous notes deemed necessary such as irregular PPG waveform due to participant movement
 - NOTE: All keys are labeled with their function on the keyboard itself
- The clinical operator/technician will save the entire session with the following naming convention:
 - RA-C01_TreatmentID
 - (see Treatment_ID_LookupSheet)

A dedicated directory on the desktop will be used to save the Wave PRO data for each participant

- Data will be backed up on to a dedicated secure data storage for the study

6.3.3 SIGNAL PROCESSING

Signal processing will be conducted by a blinded evaluator working under the requirements of an Analysis Charter. The laptop provided for the data acquisition and processing will be equipped with RStudio integrated development environment software as well as the R script used to extract DA ratio and systolic amplitude values.

- The evaluator will load the data from the secure data storage
- The evaluator will extract waveforms using the BSL 4.1 software and process the waveforms using a custom R script
- The evaluator must run the script and answer the prompts in the Console tab to have the script calculate the DA ratio
 - This script analyzes PPG data from .csv files, prompts the user for key waveform features, and outputs DA ratio values and systolic amplitude, as well as the PPG waveform graphs

An Analysis Charter will be used to guide the evaluator through the process of extracting the DA ratio and systolic amplitude values. The DA ratio and systolic amplitude values will be uploaded via CRF to the EDC.

6.4 DATA ACQUISITION ACS NCP-2

6.4.1 ACS DATA ACQUISITION SYSTEM DESCRIPTION

The ACS NCP-2 software (NCPPLUS) records participant PPG and EKG waveforms throughout the duration of compressions. The ACS software will serve as the dedicated PPG waveform and data extraction system to acquire waveforms that will be used to calculate DA ratio as a result of ECP compressions on the ACS NCP-2.

The ACS PPG sensor is a transmission type PPG sensor that utilizes an infrared emitter and photo diode to detect changes in blood density due to blood pressure fluctuations.

6.4.3 SIGNAL PROCESSING

After the ACS NCP-2 sessions are complete, data extraction will be conducted by the Statistician and data processing will be conducted by a blinded evaluator. Both the Statistician and blinded evaluator will be working under the requirements of an Analysis Charter.

- The Statistician will load the data from the secure data storage
- The Statistician will open each participant's ACS data file in the ACS NCP-2 Software (NCPPLUS)
- The Statistician will load the Full Disclosure page to access the test data
- The Statistician will use built-in Augmentation Cursor Screen capture all the waveforms within the 8th minute (i.e., minute 7 to minute 8) via screenshots
 - The onboard analysis tool uses 8-second strips. Each of these strips will need to be captured within the 8th minute
- The Statistician will upload the captured data to the secure data storage
- The evaluator will load the captured data from the secure data storage
- The evaluator must run the script and answer the prompts in the Console tab to have the script calculate the DA ratio
 - This script isolates PPG data from the screenshot files, analyzes the PPG data, prompts the user for key waveform features, and outputs DA ratio values, as well as the PPG waveform graphs

An Analysis Charter will be used to guide the evaluator through the process of extracting the DA ratio. The DA ratio values will be uploaded via CRF to the EDC.

6.5 PREPARATION/HANDLING/STORAGE/ACCOUNTABILITY

6.5.1 ACQUISITION AND ACCOUNTABILITY

The study site will receive both ECP devices, the Wave PRO and the ACS NCP-2, from the Sponsor.

The study site will also be provided the BIOPAC MP35 data acquisition system, paired with a BIOPAC SS4LA PPG finger transducer, for capturing PPG data.

A laptop (Windows OS) will be provided and will include the BIOPAC BSL 4.1 software bundle to interface with the BIOPAC hardware. Dedicated digital storage directories will be created to save the data files.

A flash drive storage device will be provided to back up raw data on the laptop on a daily basis.

Data will also be uploaded to a dedicated secure data storage for the study.

Consumables include EKG electrodes, stockinette material (for interfacing the compression sleeves/cuffs to the participants legs), surgical tape, and ultrasound gel (to help interface noisy EKG electrodes) will be provided by the Sponsor.

The Sponsor will also provide an air compressor that the Wave PRO will connect to, to receive compressed air.

All devices and ancillary supplies will be logged on device accountability form(s).

6.5.2 APPEARANCE, PACKAGING, AND LABELING

Shipping: Both the Wave PRO and the ACS NCP-2 will be shipped to the study site via courier. Pression will custom package all devices and supplies for safe transport. Neither of the ECP systems requires calibration prior to powering up. Installation validation (Pression protocols) will be conducted for both systems prior to participant enrollment.

Labeling for Wave PRO:

CAUTION: Investigational Device – Limited by Federal (or United States) Law to Investigational Use.

This device is manufactured and assembled by Pression LLC, [name].

Labeling for ACS NCP-2:

Per 510(k) Number K042413: ACS Model NCP-2 External Counter-pulsation Device is a noninvasive external Counter-pulsation device intended for the use in the treatment of patients

with stable or unstable angina pectoris, acute myocardial infarction, cardiogenic shock or congestive heart failure*.

*Original indications. FDA reclassified the uses of ECP devices in December 2013: Class II (special controls) when the device is indicated for the treatment of chronic stable angina that is refractory to optimal antianginal medical therapy and without options for revascularization.

Labeling for BIOPAC MP35 Data Acquisition System:

Per BIOPAC Product Sheet:

Safety:

The MP35 satisfies the Medical Safety Test Standards affiliated with IEC 60601-1. The MP35 is designated as Class I Type BF medical equipment

EMC:

The MP35 satisfies the Medical Electromagnetic Compatibility (EMC) Test Standards affiliated with IEC 60601-1-2.

Ancillary supplies:

Laptop: Windows operating system containing BIOPAC BSL 4.1 software bundle for data acquisition and R Studio for data analysis and quantification. This laptop is intended for research use, specifically for the acquisition and quantification of PPG waveforms recorded from the Pression sponsored clinical trial. Only personnel explicitly authorized by Pression LLC will be allowed to access this laptop.

EKG electrode pads: single use, commercially available for EKG leads

Stockinette: cotton interfacing layer that is commercially available to minimize abrasions

Ultrasound gel: to be used in the event of very noisy EKG signal

Surgical tape: to be used in the event of very noisy EKG signal

Flash drive storage: commercially available USB-A flash drive for backing up raw data from the laptop. The flash drive will be used specifically and exclusively for the Pression sponsored clinical study.

6.5.3 PRODUCT STORAGE

All devices and ancillary supplies are to be securely stored at room temperature and only accessed by trained and delegated study personnel. While in storage, all devices should be unplugged (not powered) and kept away from fluids or flammable sources. All devices and ancillary supplies should only be used for the purposes of the Pression sponsored clinical trial. Please contact Pression LLC or the CRO (ABio Clinical) in case of damage or misplacement of all devices and ancillary supplies.

6.6 MEASURES TO MINIMIZE BIAS: RANDOMIZATION AND BLINDING

Given the analysis methodologies and the data collection methods, the blinded evaluator who analyzes the waveforms for input to the endpoints of DA ratio and systolic unloading will not be

blinded to ECP device, but will be blinded to the participant IDs (only treatment IDs will be provided so that the treatments cannot be paired per participant) and to the sequence of ECP device used (i.e., Wave PRO used first vs. ACS NCP-2 used first). Due to the nature of the devices, participant and operator blinding to the ECP units cannot be performed.

Randomization of ECP device order will be performed within the Electronic Data Capture System once eligibility has been determined. The randomization schedule will be generated using randomly selected small block sizes to minimize bias for the single site.

6.7 STUDY INTERVENTION COMPLIANCE

The Wave PRO System and the ACS NCP-2 ECP device will be operated according to each device's Instructions for Use (IFU), this clinical study protocol, and the training packet (provided by Pression).

Any deviations will be documented on a Protocol Device electronic Case Report Form (eCRF).

6.8 CONCOMITANT THERAPY

Participants must not be currently undergoing ECP treatment or participating in any other clinical study of an investigational device or drug where treatment has not yet been completed.

Participants may need to consult with their primary care physician to discuss their health and safety regarding their participation in this clinical trial.

For participants on diuretics, medications may be taken immediately after the session. Participants are encouraged to check with their primary care physician regarding any deviations in medication scheduling.

7 STUDY PROCEDURE DISCONTINUATION AND PARTICIPANT DISCONTINUATION/WITHDRAWAL

7.1 DISCONTINUATION OF STUDY PROCEDURES AND/OR ASSESSMENTS

The site Principal Investigator or study staff may discontinue any of the protocol required study assessments or procedures at any time due to participant safety or other concerns. For any procedures not completed, the reason for discontinuation will be documented, and Protocol Deviation eCRF will be recorded as appropriate.

7.2 PARTICIPANT DISCONTINUATION/WITHDRAWAL FROM THE STUDY

Participants have the right to withdraw their consent to participate at any time during the study. In addition, the site Principal Investigator (PI) or study staff may remove participants from the study at any time if they feel it is best for the safety and well-being of the participant. Examples include:

- Significant study intervention non-compliance.
- If any clinical adverse event (AE) or other medical condition or situation occurs such that continued participation in the study would not be in the best interest of the participant.
- If the participant meets an exclusion criterion (either newly developed or not previously recognized) that precludes further study participation.

The reason for discontinuation/withdrawal will be documented on the Study Exit eCRF.

7.3 LOST TO FOLLOW-UP

A participant will be considered lost to follow-up if the participant is unable to be contacted by the study site for the follow-up phone call. The following actions will be taken if a participant fails to return the phone call:

- The site must attempt to contact the participant as soon as possible.
- Before a participant is deemed lost to follow-up, the Investigator or designee must make every effort to regain contact with the participant (3 telephone calls, and if necessary, a certified letter to the participant's last known mailing address or local equivalent methods including email). These contact attempts should be documented in the participant's medical record.
- Should the participant continue to be unreachable, the participant will be considered "lost to follow up".

8 STUDY ASSESSMENTS AND PROCEDURES

8.1 GENERAL AND ADMINISTRATIVE PROCEDURES

The summary of study assessments, procedures and their timing are also provided in Sections 1.1 and 4.1. Before conducting any non-standard of care assessments or procedures, obtain written informed consent. All screening evaluations must be completed and reviewed to confirm that potential participants meet all eligibility criteria. The Investigator will maintain a consent log to record details of all participants enrolled and to confirm eligibility or record reasons for screening failure, as applicable.

Demographic and baseline characteristic data will include sex, age, Fitzpatrick skin type, race, and predominant ethnicity. Relevant medical history and current medical conditions and medications will be recorded. Where possible, diagnoses but not symptoms will be recorded. Body weight will be measured in kilograms (kg) and body height will be measured in centimeters (cm).

8.2 EFFECTIVENESS ASSESSMENTS

Data from the investigational devices will be obtained per Sections 4.1, 6.1, 6.2, 6.3, and 6.4.

As discussed above, analysis of the PPG data will be conducted by a blinded evaluator not associated to the study investigators or sponsor and as described in the Analysis Charter. The analysis process is briefly described in section 6.3 and 6.4 and is further detailed in a dedicated data analysis document (provided by Pression).

8.3 SAFETY AND OTHER ASSESSMENTS

Adverse Events/Serious Adverse Events (SAEs) will be recorded on the Adverse Event eCRF from the time the participant signs Informed Consent until study exit. The Investigator and any qualified designees are responsible for detecting, documenting, and recording events that meet the definition of an AE or SAE in the AE eCRF and remain responsible for following up all AEs.

The participant will be asked to complete surveys after each ECP device session and again one day after completion of the study procedures.

8.4 ADVERSE EVENTS AND SERIOUS ADVERSE EVENTS

8.4.1 DEFINITION OF ADVERSE EVENT (AE)

An adverse event is any untoward medical occurrence, unintended disease or injury, or untoward clinical signs (including abnormal laboratory findings) in participants, users or other persons, whether or not related to the investigational medical device and whether anticipated or

unanticipated. This definition includes events related to the investigational medical device or the predicate, events related to the procedures involved and for users or other persons.

8.4.2 DEFINITION OF SERIOUS ADVERSE EVENT (SAE)

A serious adverse event is an adverse event that

- a) led to death,
- b) led to serious deterioration in the health of the participant, that resulted in:
 - a life-threatening illness or injury, or
 - a permanent impairment of a body structure or a body function including chronic diseases, or
 - in-patient or prolonged hospitalization, or
 - medical or surgical intervention to prevent life-threatening illness or injury or permanent impairment to a body structure or a body function,
- c) led to fetal distress, fetal death or a congenital abnormality or birth defect including physical or mental impairment

Planned hospitalization for a pre-existing condition, without serious deterioration in health, is not considered a serious adverse event.

8.4.3 CLASSIFICATION OF AN ADVERSE EVENT

8.4.3.1 SEVERITY OF EVENT

All AEs will be assessed by the Investigator(s). Guidelines for Investigators include the following:

- **Mild:** Asymptomatic or mild symptoms; clinical or diagnostic observations only; intervention not indicated.
- **Moderate:** Minimal, local or noninvasive intervention indicated; limiting age-appropriate instrumental activities of daily living (ADL).
- **Severe:** Medically significant but not immediately life-threatening; hospitalization or prolongation of hospitalization indicated; disabling; limiting self-care ADL.

8.4.3.2 RELATIONSHIP TO STUDY INTERVENTION

The Investigator, on the basis of his or her clinical judgment, should determine whether there is a reasonable possibility the study device or procedure caused or contributed to the event. Guidelines to assess relatedness of an AE are provided below:

- **Not related:** The adverse event is determined to be solely caused by the underlying disease, disorder or condition of the participant, or attributable solely to other extraneous causes (unrelated to the device, device malfunction, or the procedure).
- **Unlikely related:** The adverse event onset does not follow a sequence of time from procedure for which the event could be attributed to the administration or procedure, and/or can be attributable to the underlying disease, disorder or condition of the participant, or attributable to other extraneous causes.
- **Possibly related:** The adverse event has onset within a clinically relevant temporal relationship to exposure to the device or procedure and is more likely than not to be at least partially caused by or aggravated by the use of the device, device malfunction, or the procedure. It must also meet both of the following criteria: (1) follows a known or easily foreseen pattern of response to device use or procedure; and (2) is not fully attributable to the underlying disease, disorder or condition of the participant, or attributable to other extraneous causes. In addition, if the adverse effect is reversible upon reoperation or device exchange, and such a procedure is done, the effect disappears or lessens in severity within the expected time interval.
- **Probable or highly probable related:** The adverse event is clearly caused by the use of the device, device malfunction, or the procedure. It must meet all the following criteria: (1) has a clear temporal relationship between device exposure and onset of the event; (2) follows a known pattern of response to device use or procedure; and (3) is not reasonably attributable to the underlying disease, disorder or condition of the participant, or attributable to other extraneous causes. In addition, if the adverse effect is reversible upon reoperation or device exchange, and such a procedure is done, the effect disappears or lessens in severity within the expected time interval.

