8.4.3.3 EXPECTEDNESS

Anticipated adverse device effect is an effect which by its nature, incidence, severity or outcome has been identified in the risk assessment.

An **unanticipated** serious adverse device effect (USADE) is a serious adverse device effect which by its nature, incidence, severity or outcome has not been identified in the current version of the risk assessment.

An **unanticipated** adverse device effect (UADE) means any serious adverse effect on health or safety or any life-threatening problem or death caused by, or associated with, a device, if that effect, problem or death was not previously identified in nature, severity, or degree of incidence in the investigational plan or application (including a supplementary plan or application), or any other unanticipated serious problem associated with a device that relates to the rights, safety, or welfare of participants.

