9.3.2 SAFETY ENDPOINTS**Safety Endpoint 1:**

Occurrence of device-related Serious Adverse Events (SAEs) as reported on the case report forms.

Analysis cohort: Safety cohort.

Analysis methods:

The number of events, number of participants and proportion of participants experiencing any device-related SAE will be summarized by treatment arm. There are no hypothesis tests, but 95% CI for the proportion of participants with an event may be calculated.

Safety Endpoint 2:

Rate of device-related Adverse Events (AEs) as reported on the case report forms.

Analysis cohort: Safety cohort.

Analysis methods:

The number of events, number of participants and proportion of participants experiencing any device-related AE (including serious) will be summarized by treatment arm. There are no hypothesis tests, but 95% CI for the proportion of participants with an event may be calculated.

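### The relatedness categories in 8.4.3.2 are stricter than the section's own standard and, read literally, can leave an unforeseen device effect uncategorised and uncounted in both safety endpoints

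*Combined protocol and SAP*

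**What the plan says.** Section 8.4.3.2 opens with a broad test. The investigator is to use clinical judgment to decide "whether there is a reasonable possibility the study device or procedure caused or contributed to the event". Four categories follow, introduced as guidelines.

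- *Not related*: the event is "determined to be solely caused by the underlying disease, disorder or condition of the participant", or due solely to other extraneous causes.
- *Unlikely related*: the timing does not fit, and/or another cause can explain the event.
- *Possibly related*: the timing fits and the event "is more likely than not to be at least partially caused by or aggravated by the use of the device" (or by its malfunction or the procedure). Two further conditions are compulsory: "1) follows a known or easily foreseen pattern of response to device use or procedure", and the event is not fully attributable to another cause.
- *Probable or highly probable related*: three criteria must all be met, one of which reads "2) follows a known pattern of response to device use or procedure".

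Section 8.4.3.3 defines an unanticipated adverse device effect (UADE) as a serious effect associated with the device that "was not previously identified in nature, severity, or degree of incidence" in the investigational plan.

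Section 9.3.2 defines both safety endpoints by device-related events as reported on the case report forms. For Safety Endpoint 2 the number and "proportion of participants experiencing any device-related AE (including serious) will be summarized by treatment arm". The justification column in Section 3 sets non-device-related events aside as irrelevant. No section says which of the four categories make an event device-related for 9.3.2.

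**The concern.** The relatedness judgment decides what enters the safety endpoints, and the plan has no all-cause event endpoint that would catch what the judgment leaves out. Two of the four categories favour effects that are already recognised, whereas 8.4.3.3 expects that some device effects will not have been identified beforehand. The two sections therefore pull apart.

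The base of recognised patterns for this device is also thin. Section 1.1 reports no adverse events among 150 healthy volunteers on predecessor technology, and a head-to-head pilot of seven participants on the Wave PRO itself. What counts as known comes mainly from the risk analysis and the side-effect list for marketed systems in 2.3.1.

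At stake is whether the device-related rates can be read at face value. Two investigators could follow 8.4.3.2 faithfully, one by its opening sentence and one by its category criteria, and classify the same event differently.

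A related gap lies in 9.3.2. Results are to be given by treatment arm. The safety cohort equals the modified intent-to-treat cohort, in which 9.2 makes group assignment the randomised order, so arm could mean sequence or device. The cohort also includes anyone exposed to either device, so a per-device proportion could include people who never received that device.

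**Working it through.** The plan states no figure on this point, so there is none to reproduce. The check is of the wording.

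**Step 1: apply the four definitions literally.** The inputs, all from 8.4.3.2, are timing (fits or not), another cause (sole, possible, none), known pattern (yes or no) and easily foreseen pattern (yes or no). That gives 2 × 3 × 2 × 2 = 24 combinations. When timing does not fit, *Unlikely* always applies, together with *Not related* if another cause is the sole one. When timing fits:

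| Other cause | Pattern known | Foreseen, not known | Neither |
|---|---|---|---|
| Sole cause | Not / Unlikely | Not / Unlikely | Not / Unlikely |
| Possible | Unlikely / Possibly | Unlikely / Possibly | Unlikely only |
| None | Possibly / Probable | Possibly | **no category** |

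Exactly 1 of 24 combinations has no category. It is an event with fitting timing, nothing else to explain it and an unforeseen pattern. The 24 combinations are not equally likely, so 1 in 24 is not a frequency. The neighbouring cell, where another cause is merely possible, sends the same unforeseen effect to *Unlikely* alone.

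The more-likely-than-not condition was taken as met here. Applying it can only remove events from *Possibly*.

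**Step 2: compare with the section's own standard.** An event in either of those two cells can satisfy the opening test of a reasonable possibility that the device caused or contributed. The pattern criterion alone bars it from both related categories. The contradiction is therefore internal to 8.4.3.2.

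**Step 3: follow the event to the endpoints.** Assume that device-related means *Possibly* or *Probable*, which the plan does not state. An uncategorised or *Unlikely* event is then absent from both endpoints.

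**Step 4: illustrate the size.** About 50 participants are planned (9.3.1). The event counts and rates below are assumptions.

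- One misfiled participant: 1/50 = 2 percentage points.
- Three participants with a new effect: the literal rules would report 0/50 (exact 95% CI 0 to 7.1%) where 3/50 = 6.0% (1.3% to 16.5%) occurred.
- Chance that at least one such event occurs, 1 − (1 − p)^50: 39.5% for p = 1%, 63.6% for 2%, 92.3% for 5% and 99.5% for 10%.

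The intervals are what any study of 50 would give. They show how coarse the estimate is, not how often the gap would be used.

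**The case against.** The strongest case against is that the gap is narrow and the plan has other protections.

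- *Possibly related* also accepts an easily foreseen pattern. A reader might infer that every new effect is shut out. The text does not support that.
- The categories are guidelines under clinical judgment, and 9.3.2 does not say which of them count. A reader might infer that an unforeseen effect is certain to drop out of both endpoints. That is an inference, because an investigator could still record it as related under the opening sentence.
- Exposure is two 10-minute sessions, and 2.3.1 already lists abrasion, bruising, muscle ache, blistering, paresthesia, skin breakdown and cardiac events. All of these meet the pattern criterion.
- All adverse events go on the eCRF (8.3, 8.4.4), the sponsor assesses serious ones for UADE status (8.4.5), and the Medical Monitor evaluates any event (10.1.4).
- Safety has no hypothesis test or threshold, so one event does not decide a conclusion. The same wording also governs predicate events, so a bias against or in favour of one device is not shown.

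These points limit the reach but do not remove the contradiction. The safeguards protect detection, yet no text says that they change the endpoint count, which follows the case report forms. For non-serious new effects, only the Medical Monitor's review remains.

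On assignment between devices, a reader might infer that the two compressions come only 20 minutes apart and that local effects are asked about only on the next day. In fact setup (about 10 minutes) and rest (about 5) follow the 20-minute washout, so the gap is about 20 + 10 + 5 = 35 minutes or more, and a questionnaire follows each session (4.3, 8.3). The AE form is not in the documents, so missing fields cannot be asserted. Nor would it be right to count every late local event against both devices. The Wave PRO compresses only the calves, and such a rule would charge it with thigh or buttock effects of the predicate cuffs.

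**Conclusion.** The concern holds in limited form. Section 8.4.3.2 sets one standard and then imposes a stricter one. Under the stricter one, an unforeseen device effect may have no category, or only *Unlikely*, and so may be omitted from both safety endpoints. This rests on a literal reading of the criteria and on device-related meaning *Possibly* or *Probable*. The documents confirm neither.

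The size cannot be estimated, because no rate of unforeseen effects is given. At about 50 exposed, each affected participant is worth 2 percentage points. The endpoints are secondary and descriptive, and the primary analysis and sample size are untouched. The change is still worth making before data are collected, since a stated rule that can produce a wrong count is easily put right.

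**What to change.** In 8.4.3.2, define *Possibly related* by the section's own reasonable-possibility standard. In both related categories, make a known or foreseen pattern supporting evidence and not a required criterion.

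In 9.3.2:

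- State that *Possibly* and *Probable* count as device-related.
- Summarise by device, not by randomised sequence, with participants exposed to that device as the denominator.
- Assign events arising after the second session by onset time, body site and investigator-assessed relatedness to each device. Count an event against both devices only when it lies in a region that both compress and cannot be attributed to one.

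The cost is wording in two sections. If the AE form does not already hold onset relative to each session and relatedness to each device, it also needs those two fields. The downside is that device-related rates may be slightly higher.
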